**Name of funding source or sponsor (*please do not abbreviate*):**

not funded  Federal  State  industry  foundation  UNC-CH  
 other (specify): EPA Intramural Federal Research

**For industry sponsored research (if applicable):**

Sponsor's master protocol version #:

Version date:

Investigator Brochure version #:

Version date:

Any other details you need documented on IRB approval:

**RAMSeS proposal number** (from Office of Sponsored Research):

## Checklist of Items to Include with Your Submission

**Include the following items with your submission**, where applicable.

- Check the relevant items below and include one copy of all checked items 1-11 in the order listed.
- Also include two additional collated sets of copies (sorted in the order listed) for items 1-7.

→ **Applications will be returned if these instructions are not followed.**

Check	Item	Total No. of Copies
X	1. This application. One copy must have original PI signatures.	3
X	2. Consent and assent forms, fact or information sheets; include phone and verbal consent scripts.	3
	3. HIPAA authorization addendum to consent form.	3
X	4. All recruitment materials including scripts, flyers and advertising, letters, emails.	3
X	5. Questionnaires, focus group guides, scripts used to guide phone or in-person interviews, etc.	3
	6. Documentation of reviews from any other committees (e.g., GCRC, Oncology Protocol Review Committee, or local review committees in Academic Affairs).	3
	7. Protocol, grant application or proposal supporting this submission, if any (e.g., extramural grant application to NIH or foundation, industry protocol, student proposal). This must be submitted if an external funding source or sponsor is checked on the previous page.	1
	8. Addendum for Multi-Site Studies where UNC-CH is the Lead Coordinating Center.	1
	9. Data use agreements (may be required for use of existing data from third parties).	1
	10. Only for those study personnel not in the online UNC-CH human research ethics training database ( http://cfx3.research.unc.edu/training_comp/ ): Documentation of required training in human research ethics.	1
	11. Investigator Brochure if a drug study.	1

A.2.4. Do you plan to enroll subjects from these vulnerable or select populations: a. UNC-CH students or UNC-CH employees? b. Non-English-speaking? c. Decisionally impaired? d. Patients? e. Prisoners, others involuntarily detained or incarcerated, or parolees? f. Pregnant women? g. Minors (less than 18 years)? If yes, give age range:        to        years	X -- -- -- -- -- --	-- X X X X X X
A.2.5. a. Are sites outside UNC-CH engaged in the research? b. Is UNC-CH the sponsor or lead coordinating center for a multi-site study? If yes, include the Addendum for Multi-site Studies. If yes, will any of these sites be outside the United States? If yes, is there a local ethics review committee agency with jurisdiction? (provide contact information)	-- -- -- --	X X -- --
A.2.6. Will this study use a data and safety monitoring board or committee? If yes: UNC-CH School of Medicine DSMB? (must apply separately) Lineberger Cancer Center DSMC? Other? Specify:	-- -- -- --	X -- -- --
A.2.7. a. Are you collecting sensitive information such as sexual behavior, HIV status, recreational drug use, illegal behaviors, child/physical abuse, immigration status, etc? b. Do you plan to obtain a federal Certificate of Confidentiality for this study?	-- --	X X
A.2.8. a. Investigational drugs? (provide IND # ) b. Approved drugs for "non-FDA-approved" conditions? All studies testing substances in humans must provide a letter of acknowledgement from the UNC Health Care Investigational Drug Service (IDS).	-- --	X X
A.2.9. Placebo(s)?	--	X
A.2.10. Investigational devices, instruments, machines, software? (provide IDE # )	--	X
A.2.11. Fetal tissue?	--	X
A.2.12. Genetic studies on subjects' specimens?	X	--
A.2.13. Storage of subjects' specimens for future research? If yes, see instructions for Consent for Stored Samples.	X	--
A.2.14. Diagnostic or therapeutic ionizing radiation, or radioactive isotopes, which subjects would not receive otherwise? If yes, approval by the UNC-CH Radiation Safety Committee is required.	--	X
A.2.15. Recombinant DNA or gene transfer to human subjects? If yes, approval by the UNC-CH Institutional Biosafety Committee is required.	--	X
A.2.16. Does this study involve UNC-CH cancer patients? If yes, submit this application directly to the Oncology Protocol Review Committee.	--	X
A.2.17. Will subjects be studied in the General Clinical Research Center (GCRC)? If yes, obtain the GCRC Addendum from the GCRC and submit complete application (IRB application and Addendum) to the GCRC.	--	X
A.2.18. Will gadolinium be administered as a contrast agent?	..--	.. X

### Part A.3. Conflict of Interest Questions and Certification

The following questions apply to **all investigators and study staff** engaged in the design, conduct, or reporting results of this project **and/or their immediate family members**. For these purposes, "family" includes the individual's spouse and dependent children. "Spouse" includes a person with whom one lives together in the same residence and with whom one shares responsibility for each other's welfare and shares financial obligations.

A.3.1. Currently or during the term of this research study, does any member of the research team or his/her family member have or expect to have:
 
(a) A personal financial interest in or personal financial relationship (including gifts of cash or in-kind) with the sponsor of this study?
 
(b) A personal financial interest in or personal financial relationship (including gifts of cash or in-kind) with an entity that owns or has the right to commercialize a product, process or technology studied in this project?
 
(c) A board membership of any kind or an executive position (paid or unpaid) with the sponsor of this study or with an entity that owns or has the right to commercialize a product, process or technology studied in this project?
	
 yes  no
 
 yes  no
 
 yes  no
	

A.3.2. Has the University or has a University-related foundation received a cash or in-kind gift from the sponsor of this study for the use or benefit of any member of the research team?
	
 yes  no
	

A.3.3. Has the University or has a University-related foundation received a cash or in-kind gift for the use or benefit of any member of the research team from an entity that owns or has the right to commercialize a product, process or technology studied in this project?
	
 yes  no
	

**If the answer to ANY of the questions above is yes**, the affected research team member(s) must complete and submit to the Office of the University Counsel the form accessible at <http://coi.unc.edu>. List name(s) of all research team members for whom any answer to the questions above is yes:

---

## Part A.4. Questions Common to All Studies

*For all questions, if the study involves only secondary data analysis, focus on your proposed design, methods and procedures, and not those of the original study that produced the data you plan to use.*

**A.4.1. Brief Summary.** Provide a *brief* non-technical description of the study, which will be used in IRB documentation as a description of the study. Typical summaries are 50-100 words. *Please reply to each item below, retaining the subheading labels already in place, so that reviewers can readily identify the content.*

**Purpose:** Advanced age and common genetic polymorphism of the antioxidant enzyme glutathione-s-transferase M1 (GSTM1) appear to confer susceptibility to ambient particulate matter (PM). This study will compare responses to PM exposure in older volunteers with GSTM1 null and sufficient genotypes.

**Participants:** 30 healthy 50-75 yo subjects.

**Procedures (methods):** Subjects will be placed on a diet restricted of omega and oleic fatty acids for approximately 42 days prior to undergoing sequential exposures to air (control) and concentrated ambient PM (CAP) for 2 hr. Pulmonary, vascular and cardiac function will be evaluated pre, immediately post and 18 hr post exposure.

**A.4.2. Purpose and Rationale.** Provide a summary of the background information, state the research question(s), and tell why the study is needed. If a complete rationale and literature review are in an accompanying grant application or other type of proposal, only provide a brief summary here. If there is no proposal, provide a more extensive rationale and literature review, including references.

Numerous epidemiological studies have demonstrated an association between acute and chronic exposure to ambient levels of particulate matter (PM) and various adverse cardiopulmonary effects including mortality, respiratory tract infection, exacerbation of asthma, chronic bronchitis, ischemic heart disease, and stroke (see review, (1)). A recent national scale epidemiological study has shown that short-term exposure to particulate matter (PM) is associated with increased rates of hospital admission for cardiovascular and respiratory symptoms. The cardiovascular risk tended to be higher in the Eastern United States. This study also indicated a disproportionate risk among the elderly who are exposed to PM (2). Dietary factors such as intake of omega-3 fatty acids have been linked to human susceptibility to the adverse effects of ambient PM (14). Although air pollution exposure has long been known to be a risk factor for respiratory disease, over the last decade, a growing body of epidemiological studies has heightened concern over elevated rates of cardiovascular events related to both short-term and long-term exposure to PM (3). The risk of death from cardiovascular disease (myocardial infarction, heart failure, and fatal arrhythmias) in response to chronically high levels of air pollution was much greater than that from lung disease (4-6). Short-term elevations in ambient PM levels are capable of evoking cardiac arrhythmias, worsening heart failure, and triggering acute atherosclerotic/ischemic cardiovascular complications, particularly in certain at-risk subsets of population (3). PM exposure can result in increases in heart rate, and decreases in heart rate variability (HRV; defined as changes in mean heart rate during 24 hrs, which is a reflection of autonomic tone on the heart (7)). PM has been associated with transient increases in plasma viscosity (8), endothelial dysfunction (9) and acute-phase reactants (10, 11) such as C-reactive protein (12). Animal

studies have suggested that long-term exposure to low concentration of PM altered vasomotor tone, induces vascular inflammation and potentiates atherosclerosis (13). Despite a decade of intensive studies, much about the PM health effects problem, especially the cardiovascular effect, is still not well understood. The present study is designed to test the hypothesis that genetic expression of the Phase II metabolizing enzyme GSTM1 alters the outcome of adverse responses to PM exposure.


**A.4.3. Subjects.** *You should describe the subject population even if your study does not involve direct interaction (e.g., existing records).* Specify number, gender, ethnicity, race, and age. Specify whether subjects are healthy volunteers or patients. If patients, specify any relevant disease or condition and indicate how potential subjects will be identified.

Subjects for this study will be healthy 50-75 year-old male and female volunteers of any ethnicity and race. The study will enroll both GSTM1 null and sufficient subjects. The fraction of subjects who are GSTM1 null will be targeted to be approximately 40 %, reflecting the prevalence of this polymorphism in the general US population.

Based on recently completed studies for subjects with the characteristics sought in this study, the expected screening attrition rate is up to 70 %, with a heavy effect of genotype requirement. Post-screening completion rate is up to 50 %. Extrapolating from these rates, we can expect a 15% overall completion yield. Therefore, to obtain 30 subjects, we will enroll up to 200 subjects.

Subjects will be recruited through an on-site contract with the Westat Corporation (see section B1 below).

**A.4.4. Inclusion/exclusion criteria.** List required characteristics of potential subjects, and those that preclude enrollment or involvement of subjects or their data. Justify exclusion of any group, especially by criteria based on gender, ethnicity, race, or age. If pregnant women are excluded, or if women who become pregnant are withdrawn, specific justification must be provided.

**Inclusion criteria:**

- Age 50-75 years old generally healthy male and female.
- Normal resting ECG.
- Oxygen saturation greater than 94% at the time of physical exam.

**Exclusion criteria:**

- A history of angina, cardiac arrhythmias, and ischemic myocardial infarction or coronary bypass surgery.
- Cardiac pacemaker.
- Uncontrolled hypertension (> 150 systolic, > 90 diastolic).
- Neurodegenerative diseases such as Parkinson's and Alzheimer disease.
- History of bleeding diathesis.
- Currently taking  $\beta$ -blockers to control hypertension and/or arrhythmias.
- Use of oral anticoagulants.
- Participants must refrain from all over-the-counter NSAIDs for a period of two weeks prior to exposure. Low-dose aspirin will be acceptable. Medications not specifically mentioned here may be reviewed by the investigators prior to a participant's inclusion in the study.
- Subjects will be required to avoid taking antioxidants (e.g., beta-carotene, selenium, vitamin C, vitamin E, zinc) for approximately 6 weeks before the exposures. Calcium supplements and statins are permitted.
- Subject is pregnant, attempting to become pregnant or breastfeeding.
- No exposure will be conducted within 4 weeks of a respiratory tract infection.
- Eye or abdominal surgery (e.g., hernia surgery) within 6 weeks will be exclusionary.
- Active allergies. Seasonal allergies are not exclusive if out of season throughout participation in study.
- A history of chronic illnesses such as diabetes, cancer (non-melanoma skin cancer may be acceptable), rheumatologic diseases, immunodeficiency state, known cardiovascular disease, chronic respiratory diseases such as chronic obstructive pulmonary disease or asthma. Hypothyroid is acceptable.
- Subjects will be required to avoid taking omega-3 fatty acids for 6 weeks before the exposure day. Subjects who are on prescriptions taking omega-3 fish oil as therapy will be excluded.
- Subjects will be instructed to avoid more than one 4-6 oz/serving of all types of fish and shellfish, as well as all types of nuts, flaxseeds and flaxseed oil, rapeseed oil, canola oil,

soybeans and soy products, omega-3 fortified eggs, and cod liver oil for 6 weeks before their first exposure. Individuals who are unable to comply with these restrictions will be excluded.

- Subjects will be required to limit their use of all cooking oils, dressings, and sauces during the study and to avoid olive oil and other vegetable oils because of their oleic and omega-3 contents. Use of a cooking spray such as PAM will be allowed.
- Male subjects will be asked to refrain from using erectile dysfunction drugs 72 hrs before exposure.
- Because of reported cardioprotective effects of red wine, subjects will be prohibited from drinking red for 6 weeks prior to their first exposure.
- Subjects who are currently smoking or have smoking history within 1 year of study (defined as more than one pack of cigarettes in the past year) or smoked more than 5 pack-years in lifetime.
- Because the exposures use a facemask that could trigger headaches in sensitive individuals, subjects who suffer from migraines will be excluded from participation.

Use of other medications will be evaluated on a case-by-case basis. There is the potential that an individual's current medication use will preclude them from participating in the study at the current time, but they may be reassessed and potentially rescheduled for participation at a later time.

**A.4.5. Full description of the study design, methods and procedures.** Describe the research study. Discuss the study design; study procedures; sequential description of what subjects will be asked to do; assignment of subjects to various arms of the study if applicable; doses; frequency and route of administration of medication and other medical treatment if applicable; how data are to be collected (questionnaire, interview, focus group or specific procedure such as physical examination, venipuncture, etc.). Include information on who will collect data, who will conduct procedures or measurements. Indicate the number and duration of contacts with each subject; outcome measurements; and follow-up procedures. If the study involves medical treatment, distinguish standard care procedures from those that are research. If the study is a clinical trial involving patients as subjects and use of placebo control is involved, provide justification for the use of placebo controls.

Approximately 30 subjects will complete a regimen in which each subject will undergo exposures to clean air and to CAP sequentially on successive days. Each exposure will be 2 hours in duration with the subject at rest in a specialized exposure chamber.

The primary endpoints include HRV, pulmonary function, and biomarkers that include neutrophils, platelets, fibrinogen, C-reactive protein, lactate and plasminogen activator inhibitor. We will also assess endothelial cell function by brachial artery ultrasound. We will carefully monitor the symptoms that subjects may develop during the exposure and over a 24 hour period following exposure. The symptoms include chest pain, dyspnea, pallor, ataxia, and significant heart rhythm anomalies like rapid heartbeat or skipped beats, or arrhythmias noted on EKG. In addition, analyses of blood samples taken after exposure will be scrutinized for abnormalities, including neutrophil counts. Symptoms and/or changes detected in the genotyping blood samples that are considered clinically significant could prompt the study physicians to stop the study. To the extent possible, subjects who fall ill during their participation in the study will be rescheduled.

## Subject Qualification

**Screening:** Subjects will be recruited by the Westat Corporation (see section B1 below). During an initial telephone interview, the subjects will receive information regarding the study and their eligibility status will be assessed. Subjects whose responses indicate that they are likely to meet the criteria will be scheduled for a genetic screening appointment in the medical station in the US EPA Human Studies Facility (HSF). Depending on the need to maintain a representative population of subjects over time, GSTM1 null or sufficient subjects may be enrolled exclusively at various points in the study. At that time a genotype screening informed consent form and a consent form for storing blood with identifying information will also be signed. The subjects identified from a previous study (see page 26, methods of recruiting) will not need genotype screening. Subjects will then undergo a brief medical history screening and blood pressure measurement. Subjects will then have approximately 20 ml of blood collected. A portion of the blood will be used for genetic screening for GSTM1 sufficiency and another portion of the blood will be used for the cholesterol levels, fatty acid analysis, and biochemistry analysis. Information obtained from the blood analyses at this point could be used by the study physicians to stop a subject's participation or end the study. Subjects will be given a copy of the Medical History Form to be filled out and mailed back after they are selected on the genotype.

**GSTM1/GSTP1 genotype screening:** A portion of the blood sample (about 5 ml) will be used for genotyping of GSTM1 and other non-selective genotypic markers such as GSTP1. Total DNA will be isolated from the blood sample and polymeric chain reaction (PCR) will be run to determine if the subject carries a GSTM1 positive or null gene polymorphism.

**Physical exam:** Subjects who are not excluded during the genetic screening will be scheduled for a physical examination in the HSF. During this visit, subjects will sign an informed consent to undergo the screening procedures and physical examination as per the previously UNC IRB-approved protocol, Recruitment and Screening of Potential Participants for U.S. EPA Studies (95-EPA-66). Subjects will then undergo a physical exam, pulse oximetry, and screening/baseline 12-lead electrocardiogram (ECG). A menstrual history will be collected on all female subjects.

**Training session:** Those subjects who are not excluded on the basis of the physical exam and genetic screening will undergo a training session to familiarize them with the study protocol. At that time the study protocol will be outlined and informed consent obtained to initiate the study. Subjects will ask any questions they might have regarding their participation in the study. Subjects will then undergo spirometry for pulmonary function assessment. Subjects will also undergo a min ventilation measurement recorded while sitting at rest. Pregnancy tests will be administered to any female subjects who may have child-bearing potential on the training day and on the exposure day if more than 7 days since the last pregnancy test have elapsed.

**Dietary Restriction and Recording:** As specified above under Subject Exclusions, subjects will be required to restrict their dietary consumption of fish, seafood, oils, nuts, omega-3 fatty acid fortified foods and dietary supplements and vitamins for approximately 42 days. During their training day subjects will receive instruction on foods to avoid and on estimating dietary portions. Subjects will be asked to record their diet for two 24 hr periods, one during the week and one during the weekend, approximately midway during their dietary restriction period.

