The actual concentration of CAP will be determined retrospectively by filter gravimetry, with exposures monitored in real time with a tapered element oscillating microbalance (TEOM). Subjects will be monitored continuously by the EPA personnel by closed-circuit camera, blood pressure measurements, pulse oximetry and ECG telemetry. A duty physician will be available at all times. The subjects will be able to end their exposure and exit the chamber at any time if they choose to end their participation in the study. Blood pressure, heart rate, and oxygen saturation will be measured continuously during the exposure period. A confirmed blood O2 saturation levels less than 89 % will result in a cessation of exposure. Heart rate alarm limits will be set up for each subject and monitored continuously by the console operator and the nursing staff.

**CAP Exposures-**Concentrated particles will be generated by drawing ambient air from above the roof of the Human Studies Facility and passing the air through a 2 stage aerosol concentrator which produces up to a 20-fold increase in particle number and mass. Particles larger than about 2.5 microns will be excluded by a size-selective inlet from entering the concentrator at the rooftop intake. During the particle concentrating process, ambient air pollution gases will be diluted by a factor of four. Air temperature and humidity will be monitored and maintained to ensure proper operation of the concentrator. An air conditioner in the chamber can be utilized to both heat or cool chamber air for subject comfort. The flow of air into the chamber will be 65 liters per minute, with approximately 15 liters per minute diverted for analytical instrumentation and filter devices attached upstream from the chamber. The remaining approximately 50 L/min will be provided to the subject through a face mask. Since the air will be pulled into the chamber by a suction blower connected downstream of the chamber, the chamber will be slightly below atmospheric pressure.

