The concentration of particles delivered to the chamber will vary depending on the levels of naturally occurring particles in the Chapel Hill air. Although 24 hr averages seldom exceed 15-20 ug/m^3, peak values in the summer can be as high as 50-60 ug/m^3 with lower values during the rest of the year. A face mask is used to reduce the daily and seasonal variability of PM concentration. Our past experience provides a basis to expect the particle mass delivered to the mask will be up to 600 ug/m^3. The particle burden, on a mass basis presented to the volunteer will not exceed an exposure an individual receives over a 24 hour period while visiting a typical urban center in America on a smoggy day. The particle mass of the outdoor air entering and exiting the aerosol concentrator will be monitored continuously. Filter samples will be obtained from the devices located upstream from the chamber and analyzed for both mass and chemical composition of particles. If it is confirmed that particulate mass levels exceed 600 ug/m^3 for greater than 6 minutes, exposure will be terminated. The process for confirmation may take up to

additional 10 minutes. The shutdown procedure involves venting a valve on the exposure chamber, which markedly reduces the particle exposure, and alerting the investigator with both auditory and visual signals leading to removal of the subject from the chamber. Blood pressure, telemetry, and oxygen saturation will be measured during the exposure period.

**Immediate Post-exposure:** Subjects will be released while wearing the Holter and blood pressure monitors. Symptoms questionnaire after exposure will be collected. Blood pressure, lung function, endothelial cell function, and heart rate variability will be measured and approximately 46.2 ml of blood samples will be collected.

**Eighteen Hours Post-PM exposure:** Eighteen hours after the exposure, the subjects will return to the HSF to undergo a brief medical evaluation, including blood pressure, spirometry (pulmonary function testing) and endothelial cell function (BAU) measurements. The subject will then be allowed to relax for 20-30 minutes in a reclined position, after which a 10-minute resting HRV measurement will be obtained, and approximately 46.2 ml of blood will be taken. Holter monitor will be removed.

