Subjects will be recruited for this study by the Westat Corporation, which has recruited for studies at the U.S EPA HSF since 1998. The manner in which this will be done is similar that that of past U.S. EPA studies and specific recruitment procedures as per the previously UNC IRB-approved protocol, Recruitment and Screening of Potential Participants for U.S. EPA Studies (95-EPA-66). Every effort will be made to recruit women and members of racial minority groups into this study. Since this study will recruit older healthy subjects and one human study conducted at HSF (“Cardioprotective Effects of Omega-3 Fatty Acids Supplementation in Healthy Older Subjects Exposed to Air Pollution Particles”, [name]) also involved the same age groups, therefore we are likely to re-contact with these subjects to check if they are interested in participation in this study. Subjects will be asked to call the recruitment office. During the telephone interview, the subjects will receive information regarding the study and their eligibility for the study will be assessed. Subjects who provide responses which indicate that they are likely to meet the criteria will be scheduled for an appointment in the Medical Station in the U.S. Human Studies Facility.

**B.2. Protected Health Information (PHI).** If you need to access Protected Health Information (PHI) to identify potential subjects who will then be contacted, you will need a *limited waiver of HIPAA authorization*. If this applies to your study, please provide the following information.

- a. Under this limited waiver, you are allowed to access and use only the minimum amount of PHI necessary to review eligibility criteria and contact potential subjects. What information are you planning to collect for this purpose?
- b. How will confidentiality/privacy be protected prior to ascertaining desire to participate?
- c. When and how will you destroy the contact information if an individual declines participation?

**B.3. Duration of entire study and duration of an individual subject’s participation, including follow-up evaluation if applicable.** Include the number of required contacts and approximate duration of each contact.

It is anticipated that the duration of the study will be approximately 18 months. Participant recruitment and screening is expected to be continuous throughout the study until the intended number of participants is reached.

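### Single-genotype enrolment periods with no balancing over season or CAP concentration allow the null-versus-sufficient comparison to be confounded with particle dose

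*Protocol*

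**What the plan says.** **Enrolment.** Protocol A.4.5, Subject Qualification (Screening), opens the relevant sentence with its purpose, "Depending on the need to maintain a representative population of subjects over time", and then gives the permission: "GSTM1 null or sufficient subjects may be enrolled exclusively at various points in the study". It sets no limit on the timing or length of such periods. Section B.6 provides payment for a volunteer whose genotype turns out not to be needed, so the rule is meant to be used.

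**Dose.** A.4.5, CAP Exposures, states: "The concentration of particles delivered to the chamber will vary depending on the levels of naturally occurring particles in the Chapel Hill air". Summer peaks of 50-60 µg/m³ are given for the outdoor air, "with lower values during the rest of the year". The same section adds: "A face mask is used to reduce the daily and seasonal variability of PM concentration". The Protocol Operations Plan (section 2.0) starts dilution at about 500 µg/m³ by TEOM. It leaves the investigator to decide whether to run or reschedule when the estimate is below 50 µg/m³.

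**Duration.** B.3: "the duration of the study will be approximately 18 months".

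**Measurement and analysis.** Each subject's dose is known afterwards: "The actual concentration of CAP will be determined retrospectively by filter gravimetry". A.4.8 names ANOVA and rank sum tests, and says that about 30 subjects are enrolled so that null and positive subjects can be compared, with about 40% null.

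**The concern.** The study asks whether GSTM1 genotype changes the response to CAP. Each subject is his or her own control for air against CAP, but null and sufficient subjects are different people exposed on different dates. If one genotype is enrolled alone for a stretch and that stretch falls mainly in one season, that group receives a systematically different particle mass, and possibly a different composition. A difference in response due only to dose or season could then be read as genetic susceptibility, or a real genotype difference could be masked.

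The pace of the study makes this plausible. Thirty completers in 18 months is 30/18 = 1.67 per month if evenly spread, so a run of five subjects of one genotype lasts about 5/1.67 = 3 months, roughly a season. The stated aim of a representative mix over time controls the running total. It does not require the two genotypes to be exposed in the same seasons.

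**Working it through.** **1. The plan's own figure.** A.4.8 gives N = 15 for a 10% HRV change, SD 9%, power 0.8 and α 0.05 (two-sided assumed). A two-sample t-test needs 13.7, so 14 per group; the normal formula gives 13. A paired test with SD of the difference 9√2 needs 14.8, so 15. The stated figure is reproduced closely enough, and this point does not change it.

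**2. Inputs for the genotype contrast.** About 40% of 30 gives 12 null and 18 sufficient; SD 9% is from A.4.8.

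SE = 9 × √(1/12 + 1/18) = 3.354 points, with 28 degrees of freedom and a critical t of 2.048. Power for a true 10-point genotype difference at 12 versus 18 is 0.82.

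**3. Assumptions that are not in the documents.** There is no true genotype difference. The HRV response is proportional to mass, 10% at 400 µg/m³, so the slope is 10/400 = 0.025 points per µg/m³. There are two seasons, with delivered means of 400 and 200 µg/m³.

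Bias = 0.025 × (mean CAP mass in null − mean CAP mass in sufficient). The false-positive rate comes from the noncentral t distribution with noncentrality bias/3.354.

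| Share in high season (null / sufficient) | Mean mass (null / sufficient) | Bias (points) | Noncentrality | False-positive rate |
|---|---|---|---|---|
| 50% / 50% | 300 / 300 | 0 | 0 | 5% |
| 60% / 40% | 320 / 280 | 1.0 | 0.30 | 6.0% |
| 75% / 25% | 350 / 250 | 2.5 | 0.75 | 11% |
| 100% / 0% | 400 / 200 | 5.0 | 1.49 | 30% |

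**4. Sensitivity to the seasonal ratio.** A rough delivered ratio can be built from the protocol's figures. Off-season air at 15-20 µg/m³ times the maximum 20-fold concentration gives 300-400 µg/m³, against a diluted 500-600 in summer. The ratio is then 500/400 = 1.25 to 600/300 = 2. Without dilution the ambient ratio would be 50/20 = 2.5 to 60/15 = 4. These set summer peaks against 24-hour averages, so they are only a guide. Anchoring the 10% response at the overall mean dose instead, bias and false-positive rate are:

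| Split | Ratio 1.25 | Ratio 2 | Ratio 4 |
|---|---|---|---|
| 60/40 | 0.5; 5.2% | 1.4; 6.8% | 2.5; 11% |
| 75/25 | 1.1; 6% | 3.5; 17% | 6.4; 45% |
| Complete | 2.3; 10% | 7.1; 54% | 13.6; 98% |

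**5. Can it be adjusted afterwards?** With whole subjects, the genotype-season correlation is about 0.19 for the 60/40 split and 0.52 for 75/25. The variance inflation factors are 1.04 and 1.37, so adjustment for season is feasible. With complete separation the correlation is 1, and no model can separate season from genotype.

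**The case against.** The strongest reply is that the permission is conditional and serves a sensible purpose. It is there to hold the genotype mix near its target, and exclusive periods can correct an imbalance over time as well as create one. A reader might infer that the rule itself confounds genotype with dose. The text supports only that it can.

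Three other strong readings are tempting and are not supported:

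- **A 12-fold dose range.** Dividing 600 by 50 µg/m³ sets a termination limit against a floor that the investigator may waive. It is neither an expected spread nor a seasonal contrast. The mask, the dilution and the rescheduling of low-particle days all narrow the range. They do not close it: the mask is said to reduce seasonal variability, and dilution acts only at the top.
- **A 30% false-positive rate.** With seasons in a 2:1 ratio, this needs every null subject in the high season and every sufficient subject in the low one. Nothing in the protocol makes that likely.
- **An analysis that ignores dose.** A.4.8 names ANOVA without listing model terms and does not exclude covariates. A statistical analysis plan that is not shown may contain a dose term, so its absence from the protocol is not a finding.

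Enrolment date is also not exposure date. The diet restriction of about 42 days, the infection and allergy rules and the movable CAP days loosen the link between a short enrolment run and a season. That weakens the mechanism, but it gives no assurance of balance.

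What stands is that the enrolment rule has no safeguard for season or concentration, and that an analysis plan can repair the consequence only in part.

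**Conclusion.** The point holds as a gap in the design: genotype-exclusive enrolment is allowed, the CAP dose is seasonal, and nothing ties the two genotypes to the same seasons or concentrations. The genotype comparison can therefore be confounded with dose and season.

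The size cannot be determined from the documents, which give neither a dose-response nor the seasonal distribution of delivered mass. Under the stated 400/200 µg/m³ illustration the effect is slight for a mild imbalance (6%), moderate for a marked one (11%), and large (30%) only under complete separation. Other assumed ratios move these figures both ways. This is a cheap improvement worth making before enrolment, because the imbalance cannot be fully undone later. It does not show that the comparison is invalid as planned.

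**What to change.** **A.4.5, Subject Qualification.** Keep the option of exclusive enrolment but restrict it: the roughly 40:60 null:sufficient mix is to be held approximately within each season or calendar period of exposure dates, not only overall. Use flexible targets rather than fixed small blocks. At 1.67 completers per month a block of 5-6 would last about 3.0-3.6 months, and a post-screening completion rate of up to 50% would break it.

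**A.4.8.** Include each subject's filter-measured CAP mass as a covariate in the genotype comparison of CAP responses, for example in a model of each subject's CAP-minus-air difference. Report CAP mass and exposure season by genotype. Mass alone will not capture seasonal changes in composition, so balanced scheduling remains the main protection.

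**Cost.** The filter mass is already collected (A.4.5; Protocol Operations Plan, section 3.0). The covariate spends one degree of freedom, some eligible volunteers may wait weeks to months for a slot, and the recruiter has a second target to track. The planned N does not change. With equal seasonal mixes the dose-induced bias is 0 and the error rate returns to 5% under the model above.
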